8 GENERAL STATISTICAL METHODOLOGY

All analyses described in this document will be performed by the contract research organization Datemap GmbH, Freiburg, Germany using Statistical Analysis Software (SAS[®]) version 9.3 or higher.

8.1 General rules for data presentations

This section describes the general rules applied for all data displays, unless otherwise specified in each corresponding section.

Data listings will show all assessments included in the study database, regardless if used in specific summary tables.

8.1.1 Summary statistics of non-PK data

Clinical data will be listed and summarized using appropriate descriptive statistics:

- For continuous variables: Number of non-missing observations, mean, standard deviation, minimum, median, and maximum.
- For dichotomous or categorical variables: Number of non-missing observations, and frequency with percentage per category. Denominators for percentages are the number of subjects in the pertinent analysis set and period, unless otherwise specified.

8.1.2 Summary statistics of PK data

PK data will be listed as described in Section 7.8.4 and summarized using appropriate descriptive statistics:

- Plasma concentrations of selexipag and ACT-333679 will be summarized using number of non-missing observations, arithmetic mean, geometric mean, standard deviation (SD), standard error of the mean (SE), minimum, median, maximum and 95% CIs for the arithmetic and geometric mean.
- $C_{trough, ss}$ of selexipag and ACT-333679 will be summarized using number of non-missing observations, arithmetic mean, geometric mean, SD, SE, coefficient of variation of the observed and logarithmized data (CV, CV_{ln}) in %, minimum, median, maximum and 95% CIs for the arithmetic and geometric mean.
- $C_{max, ss}$ and $AUC_{\tau, ss}$ of selexipag and ACT-333679 will be summarized using number of non-missing observations, arithmetic mean, geometric mean, SD, SE, CV%, $CV_{ln}\%$, minimum, median, maximum, 95% CIs for the arithmetic and geometric mean.
- $t_{max, ss}$ of selexipag and ACT-333679 will be summarized using number of non-missing observations, arithmetic mean, SD, SE, CV%, minimum, median, maximum and 95% CI for the arithmetic mean.

8.2 Statistical methods

This section describes in general terms the statistical models and methods applied.

No confirmatory hypothesis testing will be conducted in this study. All tests and CIs will be of descriptive nature. Confidence levels are chosen as 90% for PK geometric means and 95% for all other confidence levels and will not be adapted for multiplicity.

$C_{trough, ss}$, $C_{max, ss}$, and $AUC_{\tau, ss}$, values are assumed to be log-normally distributed.

8.2.1 Statistical methods for discrete data

8.2.1.1 *Exact Pearson-Clopper CIs for the incidence of AEs*

Due to the small number of subjects included in the trial, broader estimates for the incidence rates of AEs need to be computed. The Pearson-Clopper method yields exact, while conservative confidence limits, i.e., the CI is at least 95%. They will be computed using PROC FREQ as shown below, assuming the input dataset contains counts for each *aedecod*, with 0 indicating subjects without event and 1 indicating subjects with event.

```
PROC FREQ data=<input_dataset>;
BY aedecod;
TABLES event /exact binomial (level='1');
WEIGHT count;
RUN;
```

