STATISTICAL METHODOLOGY	
Approximately 20 patients will be enrolled. In the GRIPHON Phase 3 pivotal study of selexipag, a proportion of 7.5% of patients on selexipag prematurely discontinued the study (i.e., without a morbidity/mortality event) due to prostacyclin-associated AEs. It is expected that the proportion of discontinuations will not be higher than 10%.
 
The statistical analysis will be mainly descriptive, i.e., no hypotheses will be formally tested.
 
Four analysis sets are defined in this study:
 
• Screened Analysis Set includes all subjects who are screened and have a subject identification number.• i.v. Safety Set comprises all subjects who received at least one dose of i.v. study treatment.• Safety Set (SAF) includes all enrolled (included in the study on Day 1) subjects who receive at least one dose of selexipag (oral or i.v.).• Pharmacokinetic Analysis Set (PKS) comprises all subjects included in the SAF who received the 3 doses of i.v. study treatment and who complied with the protocol sufficiently and did not deviate from the protocol in a way that might affect the PK outcome of the study. 
The study comprises 3 main periods for analysis: Period 1, Period 2, and Period 3 and follow-up. AEs and SAEs will be tabulated, for the Safety Set and i.v. Safety Set, overall across periods as well as by study period. The proportion of discontinuations due to prostacyclin-associated AEs will be

	
tabulated for the i.v. Safety Set and the SAF to address the primary objective. Due to the sample size, the proportion will be provided with a conservative 95% Clopper-Pearson confidence interval based on exact methods.
 
All secondary safety endpoints will be listed and tabulated in Safety Set and i.v. Safety Set.
 
Exposure will be summarized.
 
ECG abnormalities and laboratory variables will be descriptively summarized, both longitudinally across the study periods as well as separately per period. Death will be summarized by cause, by period, and overall.
 
The proportion of patients in each WHO FC (I, II, III and IV) will be tabulated at baseline and post-baseline, as well as the change in WHO FC at all assessed time points. Also the absence of worsening in WHO FC will be tabulated (i.e., patients that are either stable or improve).

--	---

PROTOCOL

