10.3.4 Analysis of the safety variable(s)

The study comprises 3 main periods for analysis, Period 1 (Uptravi, pre-treatment), Period 2 (i.v. selexipag; treatment period) and Period 3 (Uptravi; post-treatment).

Tolerability and safety analyses will be carried out descriptively on the SAF and the i.v. Safety Set. AEs that occur prior to first intake of Uptravi on Day 1 as a result of study-mandated procedures will be analyzed descriptively in the Screened Analysis Set. All AEs and SAEs will be coded using MedDRA.

The number and percentage of subjects experiencing AEs by period [as per [Table 4](#)] will be tabulated by MedDRA System Organ Class (SOC) and individual Preferred Term (PT) within each of the SOCs, in descending order of incidence of SOC, alphabetical order of PT, PT descending order of incidence and alphabetical order of PT for each period separately. AEs and SAEs will be tabulated, for the SAF and i.v. Safety Set overall across periods as well as by study period. The same summary applies to SAEs, AEs leading to premature discontinuation of study treatment and death. Furthermore, AEs and SAEs will be tabulated by severity and relationship to i.v. selexipag.

The proportion of discontinuations due to prostacyclin-associated AEs and AEs leading to discontinuation will be tabulated for the SAF and i.v. Safety Set (as well as all other discontinuations, irrespective of reason). Due to the small sample size, estimates of the proportion will be provided with a conservative 95% Clopper-Pearson CI based on exact methods.

Safety endpoints will be listed and tabulated in the SAF and i.v. Safety Set, overall and by study period [see [Table 4](#) for details]. Treatment exposure will be summarized. Selexipag dose (oral and i.v.) will be summarized by visit, number of subjects and percentage. Shift tables between oral and i.v. dose will also be provided.

ECG abnormalities and laboratory variables will be descriptively summarized, both longitudinally across the study periods as well as separately per period. Death will be summarized by cause, by period, and overall.

All laboratory test assessments will be listed by subject, for all subjects in the SAF and will be tabulated on the SAF and i.v. Safety Set. Descriptive summary statistics by visit will be provided for observed values and absolute changes from baseline.

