2.5 Sample Size

No confirmatory statistical tests are planned in the study.

Approximately 20 subjects will be enrolled to have at least 18 subjects in the i.v. Safety Set. In the GRIPHON Phase 3 pivotal study of selexipag, a proportion of 7.5% of subjects prematurely discontinued the study (i.e., without a morbidity/mortality event) due to prostacyclin-associated adverse events (AEs) across the titration and maintenance phases. It is expected that the proportion of early discontinuations during the entire study will not be higher than 10% (i.e., that approximately 18 subjects will enter the i.v. period).

A sample size of 18 subjects in the i.v. Safety Analysis Set will ensure that, if the true rate of discontinuations due to prostacyclin-associated AEs is between 5% and 10%, the half-width of the 95% confidence interval (CI) will be below 35%.

The precision achieved with a sample size of approximately 18 subjects in the i.v. Safety Set is considered adequate for this study (e.g., the upper boundary of the CI for the i.v. Safety Analysis Set excludes values above 35%, and for the Safety Analysis Set, above 32%).

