7.2.2 Analysis

The start date/time of the AE record from the CRF will be used to assign the AE to a study period.

Summary tables will be prepared as described in [Table 8](#) for the periods mentioned in [Table 7](#), except for the screening period.

Summary tables by SOC and PT will display the number and percentages of subjects with at least one AE in the respective primary SOC and at least one AE at the PT level. Summaries will be sorted by descending total frequency of SOCs and PTs and alphabetically in case of ties.

Summary tables by PT will display the number and percentages of subjects with at least one AE in the respective PT. Summaries will be sorted by descending total frequency of PTs and alphabetically in case of ties.

AEs occurring during the Screening period, i.e., prior to first dose of Uptravi on Visit 2 Day 1, will be listed.

Due to the small number of subjects, conservative 95% Clopper-Pearson CIs for the proportions will be computed using exact methods.

All AEs occurring during the study from date of informed consent signature to EOS will be listed.

For any injection site reaction (irrespective of clinical significance), the worst grade, criteria of the injection site reaction, as well as its clinical significance will be summarized. Any AEs associated with clinically significant injection site reactions will be summarized by PT and by maximum intensity in the AE table.

Table 8 Overview of adverse event analyses

Category	Approach
All AEs	
- N (%) of subjects having at least one AE by primary SOC and PT- N (%) of subjects having at least one AE by PT- N (%) of subjects having at least one AE by PT and maximum intensity- Listing
SAEs	
- N (%) of subjects having at least one SAE by PT- Listing
Injection site reaction AEs	
- N(%), grade and diagnosis criteria of injection site reactions- N (%) of subjects having at least one clinically significant injection site reaction by PT and maximum intensity- Listing of PTs and specific details
Prostacyclin-associated AEs	
- N (%) of subjects having at least one prostacyclin associated AE by PT- N % of subjects having at least one prostacyclin associated SAE by PT- N % of subjects having least one prostacyclin associated AE leading to discontinuation of study drug by PT- Listing

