12.7.3 Prostacyclin-associated adverse events

Output name	Display*	Title (Description)	Analysis set(s)**	Key deliverable	Mock layout
AE_PC_PT	T	Incidence of prostacyclin-associated adverse events by period and preferred term	SAF ivSAF#	Y	T_AE_PT
SAE_PC_PT	T	Incidence of prostacyclin-associated serious adverse events by period and preferred term	SAF ivSAF#		T_AE_PT
AE_PCDC_PT	T	Incidence of prostacyclin-associated adverse events leading to discontinuation of study treatment by preferred term	SAF ivSAF#		T_AE_PT

* T=Summary table, L=Listing, F=Figure, **SCR=Screened analysis set, SAF=Safety analysis set, ivSAF=i.v. Safety analysis set, PKS=Pharmacokinetic analysis set, # Tables will run on SAF only if SAF and ivSAF are identical.

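### The printed SAS code for the exact AE intervals gives no limits at zero events and does not cover the row that carries the main tolerability endpoint

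*SAP*

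**What the plan says.** **Commitment to the interval.** The protocol synopsis says the proportion of discontinuations due to prostacyclin-associated AEs will be "tabulated for the i.v. Safety Set and the SAF to address the primary objective". Protocol 10.3.4 adds that "estimates of the proportion will be provided with a conservative 95% Clopper-Pearson CI based on exact methods". SAP 7.2.2 repeats this for AE proportions in general: "conservative 95% Clopper-Pearson CIs for the proportions will be computed using exact methods". None of these passages makes an exception for zero events.

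**Implementation.** SAP 8.2.1.1 gives the only code: "They will be computed using PROC FREQ as shown below, assuming the input dataset contains counts for each" preferred term, with event coded 1 or 0. The block has `BY aedecod;`, asks for the binomial interval of `level='1'`, and ends with `WEIGHT count;`, with no option on the weight statement.

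**Output.** SAP 12.7.3 carries the endpoint in AE_PCDC_PT, "Incidence of prostacyclin-associated adverse events leading to discontinuation of study treatment by preferred term", on shell T_AE_PT. That shell opens with a row for subjects having at least one AE, followed by preferred-term rows. Every row has a 95% CI in both dose-cohort columns and in the total. T_AE_SOC has the same layout with system organ class rows added.

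**Sample size.** SAP 2.5 states: "Approximately 20 subjects will be enrolled to have at least 18 subjects in the i.v. Safety Set". It justifies this by the upper bound of the interval (35% in the i.v. Safety Set, 32% in the Safety Set).

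**The concern.** Two gaps appear when the block is followed as printed.

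1. **Zero count.** `PROC FREQ` ignores records with zero weight unless `ZEROS` is given on the weight statement. If no subject has the event, level 1 does not exist for the procedure, whether its record has count 0 or is absent. A request for the interval of level 1 then returns nothing.
2. **Headline row.** The block runs once per value of `aedecod`. The at-least-one-event row is not a value of `aedecod`, and neither are the system organ class rows. The main tolerability endpoint is read from the headline row, and no code is given for it.

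At stake is the upper limit in the case where no subject discontinues for this reason. With 0/18 the point estimate is 0%, and the upper limit is the only statement of precision the endpoint has. It is also the quantity on which the sample size was justified.

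**Working it through.** **Inputs.** Confidence level 95%, two-sided, exact (SAP 7.2.2). n = 18 in the i.v. Safety Set and about 20 in the Safety Set (SAP 2.5). Planning range for the true rate 5% to 10%, and a reference rate of 7.5% from the earlier pivotal study (SAP 2.5). Group A has 5 to 8 subjects and Group B 12 to 15 (SAP 2.1).

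**Step 1: reproduce the plan's figures.** For x events in n, the Clopper-Pearson limits are the 2.5% quantile of Beta(x, n−x+1) and the 97.5% quantile of Beta(x+1, n−x).

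- 2/18: 1.38% to 34.71%
- 2/20: 1.23% to 31.70%

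These match the stated bounds of 35% and 32%, which are not in dispute.

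**Step 2: the interval at zero events.** The lower limit is 0 and the upper limit is 1 − 0.025^(1/n).

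| n | Upper limit for 0/n |
|---|---|
| 5 | 52.2% |
| 8 | 36.9% |
| 12 | 26.5% |
| 15 | 21.8% |
| 18 | 18.5% |
| 20 | 16.8% |

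**Step 3: how likely zero discontinuations are.** P(0) = (1−p)^n.

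| True rate | n = 18 | n = 20 | Rank of zero among the possible counts, n = 18 |
|---|---|---|---|
| 5% | 0.95^18 = 39.7% | 35.8% | first (one event: 37.6%) |
| 7.5% | 0.925^18 = 24.6% | 21.0% | third (one: 35.9%, two: 24.7%) |
| 10% | 0.90^18 = 15.0% | 12.2% | fourth (one: 30.0%, two: 28.4%, three: 16.8%) |

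At n = 20 and 5%, zero is second to one event (37.7%).

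The true rate could lie below 5%. The 7.5% covers titration as well as maintenance, protocol 1.4 says these events typically arise during titration, and enrolled subjects have been on an unchanged dose for at least 28 days. The documents give no figure for such a rate. If it were 1% to 2.5% (an assumption), P(0) at n = 18 would be 83% to 63%.

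**Step 4: cohort columns of displayed rows.** For a row whose true rate is 5% to 10%, the chance that a cohort has no case is:

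- Group A: 77% to 59% with 5 subjects, 66% to 43% with 8.
- Group B: 54% to 28% with 12 subjects, 46% to 21% with 15.

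These are not conditional on the row being displayed. A simpler argument needs no rate: any displayed row with exactly one affected subject has a zero in one of its two cohort columns.

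**Step 5: is there a rule elsewhere?** The notes to T_PWDS and T_PWDT ask for every listed category to be shown even when empty, and the note to T_PK_MM says what to print where nothing can be estimated. The notes to T_AE_PT and T_AE_SOC cover sorting and period labels only, and say nothing about zero events.

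**The case against.** The strongest reply is that the method is right and binding. Protocol 10.3.4 and SAP 7.2.2 require the exact interval without exception, and the shells have a cell for it in the headline row. A blank would contradict the SAP's own text and be easy to see. SAP 8.2 describes itself as giving methods in general terms, the block uses a placeholder dataset and has no cohort or period handling, and SAP 10.4 leaves derivation details to a programming specification. On this view the block is a sketch that any competent programmer would complete. All intervals are descriptive, so no decision depends on them. The SAS behaviour was also not run.

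Much of this stands. A reader might infer that the plan gives the endpoint no upper bound. The documents do not support that, because the commitment remains and the limit has a closed form. A reader might also infer that zero is among the most likely results across the planning range. At n = 18 it is the most likely count only near 5%. Nor do terms that no subject reports lose an interval: they need no row in a preferred-term table. Nothing in the documents shows that a blank cell would be read as absence of risk.

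What does not stand is treating the block as merely illustrative. The wording for this block commits to the code as printed, whereas the `PROC MIXED` blocks in 8.2.2 are introduced as code similar to what will be run. Appendix F records that version 2.0 removed printed code from 8.2.2.4 because it would have given an incorrect analysis, so the sponsor treats printed code as something that must be right. The absence of code for the headline row can be seen from the text alone and does not depend on how SAS behaves.

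**Conclusion.** The point holds in a narrow form. The interval method, the endpoint and the sample-size bounds are all correct. The printed code does not deliver the promised interval when there are no events, and it does not address the row that carries the main tolerability endpoint.

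Over the planning range of 5% to 10%, the chance of zero discontinuations is 39.7% to 15.0% at n = 18 and 35.8% to 12.2% at n = 20. The limits left out would be 18.5% and 16.8%, both tighter than the 35% and 32% used to justify the sample size. Zero cells are also common in the dose-cohort columns.

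The zero-count part rests on standard `PROC FREQ` behaviour, which was not run for this review. The probabilities assume independent subjects with a common rate.

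This should be corrected, but it is a fault in implementation and not in the choice of analysis. It does not threaten the study's conclusions if the programmer follows SAP 7.2.2 and the shells instead of the code.

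**What to change.** In SAP 8.2.1.1:

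1. Replace the weight statement with `WEIGHT count / ZEROS;`.
2. Specify that the input holds both event levels (0 and 1) for every displayed row (headline, system organ class, preferred term), every cohort and the total, and every period, and that the `BY` statement identifies these.
3. Add one sentence: the headline rows of AE_PCDC_PT, AE_DC_PT, SAE_ALL_PT and AE_PC_PT are always printed with the exact 95% CI, including when no subject has an event (0/18: 0.0–18.5%; 0/20: 0.0–16.8%).

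A run on a dummy dataset with 0/18 should return 0.0–18.5% and would settle the software question. The cost is one option, a completed input dataset and one sentence in the SAP. No data collection or protocol change is needed.

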8.2.2 Statistical methods for continuous data

8.2.2.1 *Differences between periods in $C_{max, ss}$ and $AUC_{\tau, ss}$ of selexipag/ACT-333679*

Within each dose level and after dose normalization, differences between the Utravi and i.v. selexipag periods will be analyzed by computing the geometric mean ratios of the respective period with the oral formulation as reference treatment in the denominator. This is done by fitting a mixed linear model to the log-transformed $C_{max, ss}$ and $AUC_{\tau, ss}$ values with period as fixed and subject as random effect. The Kenward-Rodgers method for calculation of degrees of freedom will be used to obtain degrees of freedom to calculate CIs. An unstructured covariance matrix will be assumed. The difference of the least squares mean and its 90% CI will be computed and transformed back to normal scale to obtain the geometric mean ratio. SAS® code similar to the code shown below will be used:

```
PROC MIXED data=<input_dataset>;
CLASS period;
MODEL log_response=period / DDFM=KR;
RANDOM intercept /subject=usubjid TYPE=UN;
ESTIMATE 'Difference i.v. - oral' period -1 1 /CL ALPHA=0.1;
RUN;
```

8.2.2.2 *CV_b in C_{max, ss} and AUC_{t, ss} of selexipag/ACT-333679*

The CV_b expressed in percent will be computed using the formula

$$CV_b [\%] = 100\sqrt{e^{S_b^2} - 1}$$

where S_b² is the MSE of the residuals from the mixed effects model described in Section 8.2.2.1.

8.2.2.3 *Dose proportionality of AUC_{t, ss} of selexipag/ACT-333679*

To assess dose proportionality of selexipag the power model approach will be used:

The power model approach specifies a relationship between the scheduled dose D of i.v. selexipag and AUC_{t, ss} of selexipag / ACT-333679 which is expressed as

$$Y_{ij} = \alpha_j' * D_i^\beta * \varepsilon'_{ij}$$

Together with α' denoting $\exp(\alpha)$ and ε'_{ij} denoting $\exp(\varepsilon'_{ij})$, logarithmizing both sides of the equation yields a linear model

$$\log(Y_{ij}) = \alpha_j + \beta \log(D_i) + \varepsilon_{ij}$$

with

Y_{ij} AUC_{τ, ss} of dose level i in subject j (i=1, ..., I), (j=1, ..., n)

α_j intercept parameter (assumed to be a random effect)

β the slope parameter

D_i size of dose level i

ε_{ij} random error term of subject j in dose level i.

This model equation can be fitted using a mixed linear model with $\log(D_i)$ as a covariate and subject as random effect. The 90% CI for the parameter estimate for the covariate will be computed. In case of dose proportionality, 1 should be included in the 90% CI of the parameter estimate.

SAS® code similar to the following will be used:

```
PROC MIXED data=<input_dataset>;  
  MODEL log_response=log_dose / DDFM=KR S CL ALPHA=0.1;  
  RANDOM intercept /subject=usubjid TYPE=UN;  
  RUN;
```

The assessment of dose proportionality using the power approach will only be conducted when at least three dose levels are included into the study.

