7.8.4.2 Trough concentrations

Selexipag and ACT-333679 $C_{\text{trough, ss}}$ will be listed by dose, subject, and period as well as the ratio of the periods per subject.

Summary statistics will be provided by dose, including dose normalized, and by period. Implausible $C_{\text{trough, ss}}$ values will be flagged in the listings and not included in summary statistics.

7.8.4.3 $C_{\text{max, ss}}$, $t_{\text{max, ss}}$, and $AUC_{\tau, ss}$

$C_{\text{max, ss}}$, $t_{\text{max, ss}}$, and $AUC_{\tau, ss}$ of selexipag and ACT-333679 will be listed by dose, subject, and period. The ratio of the parameters between i.v. selexipag (test treatment) and Uptravi (reference treatment) per subject will be shown, except for $t_{\text{max, ss}}$. Any values

obtained from implausible plasma concentrations of selexipag or ACT-333679 will be flagged in the listings and not included in the statistical analysis.

Summary statistics will be provided by dose and period for selexipag and ACT-333679.

Dose-normalized $C_{max, ss}$ and $AUC_{\tau, ss}$ will be listed and summarized by period as well for selexipag and ACT-333679.

$C_{max, ss}$ and $AUC_{\tau, ss}$ ratio of ACT-333679/selexipag will be listed by dose, subject, and treatment and will be summarized by dose and treatment.

The ratio of $C_{max, ss}$ and $AUC_{\tau, ss}$ of selexipag and ACT-333679 between Uptravi and i.v. selexipag, after dose normalization, within each dose level (if sufficient subjects are enrolled per level) will be estimated by fitting a mixed effect model to the data using period (i.e., treatment) as fixed, and subject as random effect to the log-transformed $C_{max, ss}$ and $AUC_{\tau, ss}$ values. The ratios of geometric means between i.v. selexipag (test treatment) and Uptravi (reference treatment) will be computed and displayed together with their 90% CI by back-transforming the period contrasts and interval boundaries of the log-transformed data. If dose-proportionality is shown within each dose, then an overall model may be considered for robustness.

The inter-subject coefficient of variation (CV_b) of $C_{max, ss}$ and $AUC_{\tau, ss}$ of selexipag and ACT-333679 will be computed by using the mean squared error (MSE) of the mixed model as an estimate of variation.

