Ratio of geom. means (i.v./p.o)	xxx (xx.x, xx.x)	xxx (xx.x, xx.x)
90% CI	x.xxxx, x.xxxx	x.xxxx, x.xxxx
CV b[%]	xx.x	xx.x
CI = Confidence interval, n.e. = not estimable. p.o. = per os, b.i.d. = twice daily; i.v. = intravenous		
Geometric mean ratios were obtained by computing the anti-log of the treatment group difference of a mixed model with treatment as fixed and subject as random effect to the log-transformed data. CV_b[%] was computed using the mean squared error of residuals as a measure of variation. Values obtained from implausible plasma concentrations are not included in the analysis.		
Output: <Output name>, Produced by DATAMAP on ddMMMyyyy hh:mm (CET),		
SDTM Date: ddMMMyyyy		
Program: /<folder>/<program_name>.sas		
Page x of y		

Programming note: Display all dose levels. For dose levels not sufficiently populated to allow an estimation populate only 'n' row and show 'n.e.' for the remaining statistics.

T_PK_POW

ACT-293987

Protocol: AC-065A309

Dose proportionality of AUCtau of <selexipag/ACT-333679> after i.v. selexipag: Power model estimation

Analysis Set: Pharmacokinetic Analysis Set

n	beta	SE(beta)	90% CI
xxx	x.xxx	xx.xxxx	x.xxxx, x.xxx

CI = Confidence interval

Dose proportionality will be assumed if beta is close to 1, i.e., if the CI of beta includes 1.

Values obtained from implausible plasma concentrations are not included in the analysis.

Output: <Output name>, Produced by DATAMAP on ddMMMyyyy hh:mm (CET),

SDTM Date: ddMMMyyyy

Program: /<folder>/<program_name>.sas

Page x of y

Programming note: Produce table only if sufficient subjects are included in at least three dose levels.

T_PK_WIL

ACT-293987

Protocol: AC-065A309

Location shift analysis of tmax, ss of <selexipag/ACT-333679>

Analysis Set: Pharmacokinetic Analysis Set

n	i.v. selexipag - Uptravi Median	90% CI	p-value
xxx	x.xxx	x.xxxx, x.xxx	x.xxxx

CI = Confidence interval from a Hodges - Lehmann estimation.

p-value is derived from a Wilcoxon signed rank test.

Values obtained from implausible plasma concentrations are not included in the analysis.

Output: <Output name>, Produced by DATAMAP on ddMMMyyyy hh:mm (CET),

SDTM Date: ddMMMyyyy

Program: /<folder>/<program_name>.sas

Page x of y

[figure not shown]
F EXP

ACT-293987

Protocol: AC-065A309

Shift in selexipag dose between oral and i.v. treatment

Analysis Set: i.v. Safety Analysis Set

Output: <Output name>, Produced by DATAMAP on ddMMyyyy hh:mm (CET),

SDTM Date: ddMMyyyy

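### The SAP's mixed model for the i.v./oral ratio is not the unstructured model its text names: in a dose level whose oral/i.v. sample covariance is zero or negative, it switches without notice to an unpaired 90% CI

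*SAP*

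**What the plan says.** SAP section 7.8.4.3 estimates the i.v./oral ratio of Cmax,ss and AUCtau,ss, for selexipag and ACT-333679, "using period (i.e., treatment) as fixed, and subject as random effect to the log-transformed" values. This is done "within each dose level (if sufficient subjects are enrolled per level"), and no number is attached to sufficient.

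Section 8.2.2.1 repeats the model, names Kenward-Roger degrees of freedom and adds: "An unstructured covariance matrix will be assumed". The code below it is introduced by "SAS® code similar to the code shown below will be used". Its working lines are "MODEL log_response=period / DDFM=KR", "RANDOM intercept /subject=usubjid TYPE=UN" and "ESTIMATE 'Difference i.v. - oral' period -1 1 /CL ALPHA=0.1". There is no REPEATED statement and no NOBOUND option.

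The results go into PK_MM_SEL and PK_MM_ACT, both marked as key deliverables in section 12.8. The programming note for T_PK_MM in Appendix E reads: "Display all dose levels. For dose levels not sufficiently populated to allow an estimation populate only 'n' row". It gives no minimum n. The same table has a pooled dose-normalized row, and each row also prints a CV_b. Section 8.2.2.2 computes that CV_b from the residual MSE of this model.

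**The concern.** TYPE=UN acts on the random-effects matrix, and with one intercept that matrix is 1x1. The fitted model is therefore one subject variance plus one common residual: equal variances in the two periods and a non-negative covariance. That is bounded compound symmetry, not an unstructured 2x2 matrix.

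The bound matters because the model is fitted within dose levels that will be small. Group A has 5 to 8 subjects over five levels, a mean of 1.0 to 1.6 per level. Group B has 12 to 15 over three levels, a mean of 4 to 5. At such sizes the sample covariance of a subject's two values can be negative by chance even when the true correlation is clearly positive. The subject variance is then estimated as zero and the pairing drops out.

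T_PK_MM would then hold paired and unpaired intervals under one footnote, with nothing to tell them apart.

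**Working it through.** The plan states no correlation, precision or sample size for this analysis, so there is no planned figure to reproduce.

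**Inputs.** From the SAP: the model and code (8.2.2.1), two-sided 90% intervals, and the group sizes (2.1). From Protocol section 1.2.4: 95% CIs of the geometric mean AUC in 18 healthy subjects. Assumed: the within-subject oral/i.v. correlation ρ on the log scale, taken as 0.5 to 0.9, with 0 as a limiting case.

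**The two branches.** Let s1² and s2² be the sample variances of the oral and i.v. log values in a level with n complete pairs, and s12 their sample covariance.

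- Paired analysis: SE² = (s1² + s2² − 2·s12)/n, with n−1 df.
- Printed code, s12 > 0: the same.
- Printed code, s12 ≤ 0: subject variance 0, SE² = (s1² + s2²)/n, with 2n−2 df.

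A bounded REML fit at n = 4 showed both branches. With negative covariance the SE was 0.2947, the unpaired value, against a paired 0.3368. With positive covariance it was 0.1696, equal to the paired value.

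**Width.** When s12 ≤ 0 the unpaired SE cannot exceed the paired one, and the t quantile is smaller. The quantile ratio alone is 2.920/6.314 = 0.46 (n = 2), 2.132/2.920 = 0.73 (n = 3), 1.943/2.353 = 0.83 (n = 4) and 1.860/2.132 = 0.87 (n = 5). A switched interval is therefore always narrower than the paired one.

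**Probability of the switch.** With equal SDs, P(s12 ≤ 0) = P(F with n−1, n−1 df < (1−ρ)/(1+ρ)). At ρ = 0.5 the limit is 0.5/1.5 = 1/3:

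- n = 2: (2/π)·arctan(√(1/3)) = 1/3, or 33%.
- n = 3: (1/3)/(1 + 1/3) = 25%.

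**Coverage.** By simulation with equal SDs:

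| n | P(switch), ρ 0.5 to 0.9 | Median width ratio, ρ = 0.5 | Overall coverage, ρ 0.5 to 0.9 | Overall coverage, ρ = 0 |
|---|---|---|---|---|
| 2 | 33% to 14% | 0.36 | 87.5-89% | 85.7% |
| 3 | 25% to 5% | 0.62 | 88.5-89.7% | 86.2% |
| 4 | 20% to 2% | 0.73 | 89-90% | 86.6% |
| 5 | 16% to 1% | 0.79 | 89-90% | 86.8% |
| 18 (pooled) | 1.5% to about 0% | – | about 90% | 88.3% |

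At ρ = 0 the switch has probability 50% at any n. The paired analysis covered 90% in every cell.

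**Unequal SDs.** The Protocol 1.2.4 intervals imply log-scale SDs of ln(upper/lower)·√18/(2·2.110). For oral ACT-333679 this is ln(47.78/30.18)·4.243/4.220 = 0.46. The others are 0.54 (i.v. ACT-333679), 0.60 (oral selexipag) and 0.37 (i.v. selexipag). With the selexipag SDs, overall coverage ranged from 85.4% to 90%.

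**Number of intervals.** Each level yields 2 parameters × 2 analytes = 4 CIs. If only the three Group B levels are reported, that is 12 CIs. The expected number switched runs from 12 × 0.007 = 0.1 (n = 5, ρ = 0.9) to 12 × 0.20 = 2.4 (n = 4, ρ = 0.5). Reporting levels with 2 or 3 subjects raises the count.

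**CV_b.** In a switched row the residual MSE is (s1² + s2²)/2, the pooled total variance. Without the bound it is (s1² + s2²)/2 − s12, the within-subject residual.

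**The case against.** **Text and code need not conflict.** The covariance sentence can be read as a gloss on TYPE=UN in the RANDOM statement, since the plan specifies a random subject effect throughout. On that reading the sentence says nothing, because one intercept has no structure to choose. The wording still needs correcting, and the zero bound remains.

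**The plan has guards.** The code is only indicative, and sparse levels are to be shown as not estimable. Neither resolves the point: no minimum n is stated, and the model can be fitted at n = 2.

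**Little depends on these intervals.** This stands. SAP section 8.2 makes all CIs descriptive, no equivalence margin is set, and the primary objective is safety and tolerability.

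A reader might also infer more than the documents support:

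- *That small dose levels collapse as a rule.* They do so only when s12 ≤ 0. Otherwise, with complete pairs, code and paired analysis agree.
- *That the switched intervals are themselves too narrow.* They are narrower than the paired ones, but with equal SDs they cover about 90-95%. The shortfall belongs to the data-driven rule: at n = 2 and ρ 0.5 to 0.9, the rows that keep the pairing cover 86-89%. Switched intervals fell clearly short, at 84-85%, only with the unequal selexipag SDs at ρ = 0.9, where the switch has probability 14% at n = 2 and 0.7% at n = 5.
- *That the bound makes CV_b larger than an unbounded fit would.* The algebra above shows the reverse when s12 < 0. The fault is that the row reports total instead of within-subject variation.

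**Conclusion.** The point holds in a limited form. The covariance sentence does not describe the model in the code, and the code changes without notice from a paired to an unpaired interval in any dose level with complete pairs and a non-positive sample covariance. CV_b changes meaning in the same rows.

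The cost is modest: up to about 2.5 points of coverage at n = 2, and about 1 point or less at n = 4 and 5, for correlations of 0.5 or more with equal SDs. At zero correlation it is 3 to 4 points for n = 2 to 5. The pooled row is practically unaffected unless the correlation is low. These sizes rest on the assumed correlations and on complete pairs, which the definition of the PK analysis set makes likely. The contradiction between text and code rests on neither. This is a worthwhile correction, not a threat to the study's conclusions.

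**What to change.** Add NOBOUND to the PROC MIXED statement in section 8.2.2.1. Replace the covariance sentence with one saying that a random subject intercept with a common residual variance is fitted and that the subject variance may be estimated as negative. With complete pairs every row then gives the paired interval with n−1 df, and rows with positive covariance do not change. A stated minimum n per dose level for printing a ratio would also help.

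NOBOUND is preferable to a one-sample t on log differences. It keeps the planned mixed model, the Kenward-Roger df and the residual MSE that feeds CV_b. It also keeps any subject left with one period after implausible values are removed, whom paired differences would drop.

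The cost is one option and one sentence. A few per-level intervals, and the CV_b in those rows, become larger.
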